5.1. Overall Design

Study I9N-MC-FCAB (FCAB) is a Phase 2, multicenter, randomized, double-blind, placebo-controlled, parallel-group, outpatient study evaluating the efficacy and safety of LY3375880 SC 600 mg Q4W, 150 mg Q4W, and 50 mg Q4W as compared to placebo Q4W in adult subjects with moderate-to-severe AD. In addition, LY3375880 300mg Q4W will be evaluated in the maintenance period as described below.

The study duration will be up to 65 weeks over 4 study periods:

- Period 1: Screening Period lasting from 8 to 35 days prior to Week 0 (baseline, Visit 2).
- Period 2: Induction Period, lasting from Week 0 (baseline, Visit 2) through Week 16 (Visit 8).
- Period 3: Maintenance Period, lasting from Week 16 (Visit 8) through Week 52 (Visit 17, inclusive). At Week 16, the following will occur:
 - Responders (defined as having achieved a 50% reduction in the Eczema Area and Severity Index score [EASI-50] response, regardless of whether rescue therapy has been initiated) will undergo the following re-randomizations:
 - Subjects on any dose of LY3375880 will be re-randomized at a 2:1 ratio to either maintain their current regimen or to receive placebo until loss of response (not achieving a 25% reduction in the EASI score [EASI-25] at a scheduled visit), at which point they will restart their induction period regimen.
 - Subjects on placebo will continue receiving placebo until loss of response, at which point they will be reassigned to receive LY3375880 at 300 Q4W.
 - Nonresponders will undergo the following reassessments:
 - Subjects on 50 mg Q4W will be reassigned to 150 mg Q4W.
 - Subjects on 150 mg Q4W will be reassigned to 300 mg Q4W.
 - Subjects on 600 mg Q4W will remain on their current regimen.
 - Subjects on placebo will be reassigned to receive 300 mg Q4W.
 - Subjects with persistent disease activity, defined as not achieving EASI-25 for 3 consecutive scheduled maintenance period visits, not already on 600 mg Q4W will be reassigned to 600 mg Q4W for the remainder of the study.
- Period 4: Post-Treatment Follow-Up Period, spanning approximately 8 weeks from Week 52 (after Visit 17) to Week 60 (Visit 801).

Rescue therapy is permitted starting at Week 8 for subjects who do not achieve an EASI-25 response. Refer to Section [7.7.3](#) for details.

Treatment Arms and Duration:

[figure not shown]

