Approximately 200 subjects will be randomized 1:1:1:1 at Week 0 to 1 of 4 treatment groups in the induction period: placebo SC (Q4W), LY3375880 SC 600 mg (Q4W), LY3375880 150 mg (Q4W), or LY3375880 50 mg (Q4W). The study duration will be up to 65 weeks (Screening

Period: Up to 5 weeks; Induction Period: 16 weeks; Maintenance Period: 36 weeks; Follow-up Period: 8 weeks).

Subjects will be stratified at randomization according to disease severity (IGA [3 versus 4]) and geographic region (Japan versus non-Japan).

All procedures to be conducted during the study, including timing of all procedures, are indicated in the Schedule of Activities (Section 2). [Appendix 2](#) describes collection of laboratory samples with the list of specific laboratory tests that will be performed for this study. Study governance considerations are described in detail in [Appendix 3](#).

[Figure FCAB.1](#) illustrates the study design.

Abbreviations: R = Responders.

Response to study drug is defined as achieving an EASI-50. At Week 16, responders on LY3375880 will be re-randomized to either maintain current dosing regimen or placebo until disease recurrence (EASI-25). Placebo responders will continue on placebo until disease recurrence.

NR = Nonresponders. At Week 16, nonresponders will be reassigned to 600 mg Q4W, 300mg Q4W, or 150 mg Q4W depending on treatment group.

Note: Subjects with persistent disease activity, defined as not achieving EASI-25 for 3 consecutive scheduled maintenance period visits, not already on 600 mg Q4W will be reassigned to 600 mg Q4W for the remainder of the study.

Figure FCAB.1. Study design for Study I9N-MC-FCAB.

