7.3. Blinding

The induction period of the study is double blind. The maintenance period of the study is double blind unless a subject has persistent disease activity defined as not achieving EASI-25 for 3 consecutive scheduled maintenance period visits. In this circumstance, the subject is reassigned to 600 mg Q4W for the remainder of the study unless they were already on that regimen. Therefore, the treatment regimen can be inferred in this scenario, but will not be considered as an unblinding event as described in procedures in this section.

To preserve the blinding of the study, the unblinded site personnel qualified to prepare study drug should not be involved in any study-related procedures, and a minimum number of Lilly personnel will have access to the randomization table and treatment assignments before the study is complete.

Emergency unblinding for AEs may be performed through the IWRS, which may supplement or take the place of emergency codes generated by a computer drug-labeling system. This option may be used ONLY if the subject's well-being requires knowledge of the subject's treatment assignment. All calls resulting in an unblinding event are recorded and reported by the IWRS.

If an investigator, site personnel performing assessments, or subject is unblinded, the subject must be discontinued from the study. In cases where there are ethical reasons to have the subject remain in the study, the investigator must obtain specific approval from a Lilly clinical research physician (CRP) for the subject to continue in the study.

In case of an emergency, the investigator has the sole responsibility for determining if unblinding of a subject's treatment assignment is warranted for medical management of the event. The safety of the subject must always be the first consideration in making such a determination. If a subject's treatment assignment is unblinded, Lilly must be notified immediately. If the investigator decides that unblinding is warranted, it is the responsibility of the investigator to promptly document the decision and rationale and notify Lilly as soon as possible.

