7.7.3. Rescue Therapy

Rescue therapy is permitted **starting at Week 8** for subjects who do not achieve an EASI-25 response. If the subject meets criteria, the decision to implement rescue is according to investigator judgment and is not a requirement. Rescue therapy should only be initiated at a visit at which an EASI-25 is not met.

Choice of rescue therapy treatment

- Triamcinolone 0.1% cream and/or hydrocortisone 2.5% ointment. In the event where either of these topical formulations is not available, an alternate, equivalent potency TCS cream and/or ointment may be used.
- Investigators may also select to use TCNI and/or crisaborole where approved. If TCNI are prescribed, use should be limited to problem areas only (e.g., face, neck, skin folds, genital areas, etc.).
- On the days of study visits, topical therapy should not be applied before the subject has undergone all study procedures and clinical evaluations in order to allow adequate assessment of skin dryness.
- Subjects rescued to topical therapy will continue to take IP and use of rescue therapy will be documented in the eCRF.

In subjects who do not improve sufficiently with the prescribed provided rescue topical therapy after 7 days, a higher potency TCS may be used and IP may continue. It is recommended that if a subject reaches “clear” to “almost clear” skin after topical rescue, then medium- and/or high-potency TCS and TCNI should be stopped, and low-potency TCS (e.g., hydrocortisone 2.5% ointment) should be used once daily for an additional 7 days, then stopped. If lesions return, subjects can be retreated with TCS with or without TCNI and/or crisaborole as before at the discretion of the investigator.

If topical rescue therapy as described above fails to sufficiently control AD symptoms and if the investigator determines that a subject requires treatment with another therapeutic agent that has been demonstrated to be effective for treatment of AD but is contraindicated in this study, the subject should be discontinued from the study. In such cases, discontinuation from the study occurs prior to introduction of the new agent.

Note that subjects who receive rescue therapy during the induction period will be considered nonresponders for the primary analysis, but will undergo re-assignment/re-randomization at Week 16 based on EASI-50 response according to Section 5.1, and will not automatically be considered nonresponders for purposes of treatment assignment.

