Appendix 1. Abbreviations and Definitions

Term	Definition
AD	atopic dermatitis
ADA	antidrug antibodies
AE	adverse event: Any untoward medical occurrence in a subject or clinical investigation subject administered a pharmaceutical product that does not necessarily have a causal relationship with this treatment. An adverse event can therefore be any unfavorable and unintended sign (including an abnormal laboratory finding), symptom, or disease temporally associated with the use of a medicinal (investigational) product, whether or not related to the medicinal (investigational) product.
ALT	alanine aminotransferase
ALP	alkaline phosphatase
AST	aspartate aminotransferase
BCG	Bacillus Calmette–Guérin
blinding/masking	A single-blind study is one in which the investigator and/or his staff are aware of the treatment but the subject is not, or vice versa, or when the sponsor is aware of the treatment but the investigator and/his staff and the subject are not. A double-blind study is one in which neither the subject nor any of the investigator or sponsor staff who are involved in the treatment or clinical evaluation of the subjects are aware of the treatment received.
BSA	body surface area
CI	confidence interval
C-SSRS	Columbia-Suicide Severity Rating Scale
CSR	clinical study report
DLQI	Dermatology Life Quality Index
DNA	deoxyribonucleic acid
EASI	Eczema Area and Severity Index
EASI-25	25% reduction in the Eczema Area and Severity Index score
EASI-50	50% reduction in the Eczema Area and Severity Index score
EASI-75	75% reduction in the Eczema Area and Severity Index score

EASI-90	90% reduction in the Eczema Area and Severity Index score
ECG	electrocardiogram
eCOA	electronic Clinical Outcome Assessment
eCRF	electronic case report form
enroll	The act of assigning a subject to a treatment. Subjects who are enrolled in the trial are those who have been assigned to a treatment.
Enter	Subjects entered into a trial are those who sign the informed consent form directly or through their legally acceptable representatives.
ERB	ethical review board
FDA	Food and Drug Administration
GCP	Good Clinical Practice
HBcAb	hepatitis B core antibody
HBsAg	hepatitis B surface antigen
HBV	hepatitis B virus
HCV	hepatitis C virus
HCVAb	hepatitis C virus antibody
HIV	human immunodeficiency virus
IB	Investigator's Brochure
ICF	informed consent form
ICH	International Council for Harmonisation
Ig	immunoglobulin
IGA	Investigator's Global Assessment
IL	interleukin

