|   | • Proportion of patients achieving IGA [0]  |                                 | Maintenance                | LY3375880 600-mg or LY3375880 300-mg or LY3375880 150-mg or LY3375880 50-mg vs PBO; Week 52 | Secondary analysis   |
|   | • Proportion of patients achieving IGA [0]  | Logistic regression using NRI   | ITT                        | LY3375880 600-mg or LY3375880 150-mg or LY3375880 50-mg vs PBO; Week 16                     | Secondary analysis   |
| Eczema Area and Severity Index (EASI)                   | • EASI score
• Change from baseline in EASI score
• Percent change from baseline in EASI score                                | MMRM                            | ITT; PPS                   | LY3375880 600-mg or LY3375880 150-mg or LY3375880 50-mg vs PBO; Week 16                     | Secondary analysis   |
|   | • Proportion of patients achieving EASI50
• Proportion of patients achieving EASI75
• Proportion of patients achieving EASI90 | Logistic regression using NRI   | ITT; PPS                   | LY3375880 600-mg or LY3375880 150-mg or LY3375880 50-mg vs PBO; Week 16                     | Secondary analysis   |
| Body Surface Area (BSA) Affected by AD                  | • BSA score
• Change from baseline in BSA score  | MMRM                            | ITT                        | LY3375880 600-mg or LY3375880 150-mg or LY3375880 50-mg vs PBO; Week 16                     | Exploratory analysis |
| SCORing Atopic Dermatitis (SCORAD)                      | • SCORAD score
• Change from baseline in SCORAD score
• Percent change from baseline in SCORAD score                          | MMRM                            | ITT                        | LY3375880 600-mg or LY3375880 150-mg or LY3375880 50-mg vs PBO; Week 16                     | Secondary analysis   |
|   | • Proportion of patients achieving SCORAD75
• Proportion of patients achieving SCORAD90  | Logistic regression using NRI   | ITT; PPS                   | LY3375880 600-mg or LY3375880 150-mg or LY3375880 50-mg vs PBO; Week 16                     | Secondary analysis   |

| Measure                                | Variable   | Analysis Method (Section 5.2.3) | Population (Section 5.2.1)                              | Comparison/Time Point   | Analysis Type        |
|--|--|---------------------------------|---|---|----------------------|

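### Protocol 7.3 names one exception to the maintenance double blind, but the Section 5.1 rules let an investigator deduce active treatment in every Week 16 nonresponder and in responders after loss of response

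*Protocol*

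**What the plan says.** Protocol 7.3 says that induction is double blind and that "The maintenance period of the study is double blind unless a subject has persistent disease activity", meaning EASI-25 is missed at three consecutive scheduled maintenance visits. Those subjects go to 600 mg if not already on it. The section continues: "Therefore, the treatment regimen can be inferred in this scenario", and says that this is not to be handled as an unblinding event. Otherwise, an unblinded investigator, assessor or subject leads to discontinuation from the study unless the sponsor's physician approves continuation. Appendix 1 supplies the standard: "A double-blind study is one in which neither the subject nor any of the investigator or sponsor staff who are involved" in treatment or evaluation knows the treatment received.

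Protocol 5.1 sets the Week 16 rules. Of nonresponders (EASI-50 not met) it says, for example, "Subjects on 50 mg Q4W will be reassigned to 150 mg Q4W" and "Subjects on placebo will be reassigned to receive 300 mg Q4W". The note to Figure FCAB.1 sums up: "At Week 16, nonresponders will be reassigned to 600 mg Q4W, 300mg Q4W, or 150 mg Q4W depending on treatment group". LY3375880 responders are re-randomised 2:1 to their current regimen or placebo. Those on placebo restart their induction regimen when EASI-25 is missed at a scheduled visit. Placebo responders stay on placebo until the same event and then receive LY3375880 at 300.

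EASI is an investigator scale at every maintenance visit. Protocol 7.7.3 makes its result operational at site: "Rescue therapy should only be initiated at a visit at which an EASI-25 is not met".

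IGA 0 or 1 at Week 52 is a secondary endpoint, and Protocol 10.2.3.2 assigns it the logistic model. SAP 4.1 leaves blinding to the protocol. SAP Table FCAB.5.2 plans a Week 52 IGA comparison in the Maintenance population: "LY3375880 600-mg or LY3375880 300-mg or LY3375880 150-mg or LY3375880 50-mg vs PBO; Week 52". Protocol 10.2.1.2 says that maintenance analyses are exploratory and descriptive only.

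**The concern.** Section 7.3 makes an exception where the regimen can be worked out from the rules. The same reasoning applies, for active versus placebo, to two groups that it does not mention. If no nonresponder pathway leads to placebo, an investigator who sees that EASI-50 was missed at Week 16 knows that the subject is assigned LY3375880 from that visit. If every pathway after loss of response also leads to LY3375880, the same holds for a responder once EASI-25 has been missed.

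Three things are at stake. First, the investigator-rated maintenance scales (IGA, EASI, SCORAD) and the investigator's yes/no judgement of AE relatedness would be described as double blind where the rater can know that the subject is on active drug. Second, any subject still assigned placebo at Week 52 is in the group where the blind holds, while many subjects on active drug are not, so a Week 52 reading against placebo compares groups with different blinding. Third, 7.3 exempts only persistent disease activity from its unblinding procedure and is silent on the wider groups.

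**Working it through.** **The plan's own figure.** The documents give no share of subjects for whom active treatment is deducible. The nearest stated figure is the Week 16 power: 36% versus 8%, 50 per arm, 2-sided Fisher's exact test at 0.05, at least 90%. Exact enumeration gives 91.4%, so it reproduces. This point does not touch it.

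**Step 1: follow each pathway in Protocol 5.1.**

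| Status | Before | Assigned next |
|---|---|---|
| Week 16 nonresponder | 50 mg | 150 mg |
| Week 16 nonresponder | 150 mg | 300 mg |
| Week 16 nonresponder | 600 mg | 600 mg |
| Week 16 nonresponder | placebo | 300 mg |
| Responder after loss | kept on LY3375880 | LY3375880 |
| Responder after loss | LY3375880 withdrawn to placebo | induction regimen |
| Responder after loss | placebo throughout | 300 |

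All 4 nonresponder pathways and all 3 post-loss pathways end on LY3375880. Only a Week 16 responder who has not lost response can be assigned placebo. SAP 4.1 sends 150 mg nonresponders to 600 mg rather than 300 mg. The two documents must be reconciled, but both assignments are active, so the deduction is the same.

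The 7.3 exception lies inside these groups. A subject who misses EASI-25 three times running is either a Week 16 nonresponder or a responder who had already lost response at the first of those visits.

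**Step 2: can the site make the deduction?** The investigator scores EASI and needs EASI-25 status for the rescue decision. EASI-50 follows from the same baseline and current scores. No section masks response status or the assignment rules from the rater.

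**Step 3: what is revealed.** Only that the drug is active. Under the protocol a nonresponder may be on 150, 300 or 600 mg, and the induction arm stays masked.

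**Step 4: size.** Let a and p be the Week 16 EASI-50 rates on LY3375880 and placebo, and L the share of responders who lose response before the Week 52 rating. With 1:1:1:1 allocation, the responder share is R = (3a + p)/4 and the share with active treatment deducible is 1 − R(1 − L). The calculation assumes that all 200 subjects enter maintenance and stay on IP. The rates a, p and L are assumptions. The first row uses the planned IGA 0/1 rates as a low stand-in for EASI-50.

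| a / p | R | L = 0 | L = 20% |
|---|---|---|---|
| 36% / 8% | (1.08 + 0.08)/4 = 0.29 | 71% | 1 − 0.29 × 0.8 = 77% |
| 50% / 30% | 0.45 | 55% | 64% |
| 65% / 30% | 0.5625 | 44% | 55% |
| 80% / 40% | 0.70 | 30% | 44% |

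The range is about 30% to 77%, or roughly 60 to 154 of 200. The share passes one half only when R(1 − L) is below 0.5.

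**Step 5: who is on placebo.** With the 36%/8% stand-in, 150 × 0.36/3 + 50 × 0.08 = 18 + 4 = 22 subjects are on placebo after Week 16, all of them EASI-50 responders. The 18 are randomised against 36 kept on LY3375880. The other 4 are placebo responders who were not re-randomised.

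**The case against.** The case on the other side has real force.

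- **A reader might infer that most subjects are affected.** The documents do not support that. They give neither rate, and several scenarios above fall below one half. EASI-50 is probably met more often than IGA 0/1 and counts for re-randomisation regardless of rescue, so the first row is probably high.
- **A reader might infer that the blind is lost altogether.** It is not. In the 7.3 exception the exact regimen (600 mg) is known. Here dose level and induction arm stay masked, which matters in a dose-ranging study.
- **A reader might extend the point to itch, pain, POEM and DLQI.** Nothing reviewed says that subjects are told their EASI result, so this is not shown.
- **The statement about loss of response has exceptions.** A responder whose first loss is seen at Week 52 may have been on placebo when rated. Subjects who stopped IP remain in the study but are not on active drug, and for categorical endpoints they count as nonresponders whatever the rating.
- **A reader might infer a net bias in favour of active drug.** The direction is not established. Placebo subjects at that stage are all Week 16 responders, while the active groups contain every nonresponder. That selection works against active drug and may outweigh rater expectation. For the same reason, tabulating results by whether active treatment is inferable could not demonstrate rater bias, because that grouping is defined by poor response.
- **The consequence is limited.** Protocol 10.2.1.2 treats maintenance as descriptive. The 2:1 withdrawal comparison stays blinded up to loss of response, and Protocol 9.4.9 and 9.5 protect it by sampling all Week 16 responders at loss.

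All of this stands and narrows the point. None of it makes 7.3 accurate on active versus placebo. The descriptive label also sits beside a planned Week 52 logistic comparison with placebo in Protocol 10.2.3.2 and SAP Table FCAB.5.2.

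**Conclusion.** The point holds in limited form. Section 7.3 claims a double blind that the Section 5.1 rules do not provide for active versus placebo in Week 16 EASI-50 nonresponders and in responders after loss of response, apart from the two exceptions above. The deduction itself needs only the protocol's rules and an investigator who scores EASI. Its size, about 30% to 77% of randomised subjects by Week 52, rests entirely on assumed response and loss rates with no dropout.

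The practical consequence is for interpretation. Outside the 2:1 re-randomised LY3375880 responders before loss of response, a Week 52 result against placebo is neither a randomised comparison nor fully blinded to active versus placebo. The Week 16 primary endpoint and the other Week 16 comparisons are unaffected.

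**What to change.** (a) **Protocol 7.3.** State that active versus placebo is blinded throughout induction and, in maintenance, only for Week 16 responders up to loss of response. All other maintenance subjects are blinded to dose level at most. Extend to them the statement that 7.3 already makes for persistent disease activity, that this inference is not an unblinding event requiring discontinuation.

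(b) **SAP.** Draw blinded placebo-controlled maintenance conclusions only from the 2:1 re-randomised LY3375880 responders up to loss of response. Report the other Week 52 results, including the comparison with placebo in Table FCAB.5.2, descriptively as non-randomised, response-selected data in which active treatment can be inferred. Reconcile that table and Protocol 10.2.3.2 with the descriptive-only statement in Protocol 10.2.1.2.

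The cost is text in two documents. No new data are needed, and no dosing, reassignment or rescue rule changes. The downside is that less of the maintenance data can be called double blind.

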7.4. Dosage Modification

Not applicable.

7.5. Preparation/Handling/Storage/Accountability

IPs will be supplied by Lilly or its representative, in accordance with current good manufacturing practices, and will be supplied with lot numbers, expiry dates, and certificates of analysis, as applicable.

The investigator or his/her designee is responsible for the following:

- confirming appropriate temperature conditions have been maintained during transit for all study treatment received and any discrepancies are reported and resolved before use of the study treatment.
- ensuring that only participants enrolled in the study may receive study treatment and only authorized site staff may supply or administer study treatment. All study treatments must be stored in a secure, environmentally controlled, and monitored (manual or automated) area in accordance with the labeled storage conditions with access limited to the investigator and authorized site staff.
- the investigator, institution, or the head of the medical institution (where applicable) is responsible for study treatment accountability, reconciliation, and record maintenance (such as receipt, reconciliation, and final disposition records).

Follow storage and handling instructions stated on the IP label. Detailed instructions regarding preparation and handling of IPs will be provided by the Sponsor.

